Our preliminary data also show that collaborative participation resulted in significant but highly variable ABCDEF bundle adoption. Our next goal was to determine if collaborative participation led to increased bundle adoption. We were interested in exploring if some sites were "better" ABCDEF bundle adopters than others. The presence of a substantial amount of variability in our data would present us the opportunity to learn both from high- and low-bundle-performing sites. We calculated monthly rates of complete bundle performance, proportional bundle performance, and element-specific performance for the 17,258 patients across 49,109 full ICU days. We used segmented regression analysis for interrupted time series data to model the linear trend of bundle performance rates as a function of time for each segment (1-6 months pre-Collaborative involvement and 7-20 months during the Collaborative).

Complete bundle performance levels were low in the baseline (pre-Collaborative) period (i.e., < 4%). Complete bundle performance increased 2.0% (SE = 0.9%, $P = 0.057$) immediately after joining the Collaborative, and each month was associated with 0.6% greater increase (SE = 0.2%, $P = 0.038$) in complete bundle performance rates, compared to a relatively flat trend in the pre-Collaborative period. Proportional bundle performance rates also significantly increased by 3.8% (SE = 1.6%, $P = 0.026$) immediately after joining the Collaborative, then increased monthly at the same speed as the trend in the pre-Collaborative period (2%, SE = 0.4%, $P = 0.57$).

Bundle performance was highly variable among ICUs and across individual bundle elements; interquartile ranges of > 20% existed for all performance measures. (**Figure 1**) Elements A, C, D, and F were performed on average $\geq 70\%$ of the time at the end of the Collaborative:

Figure 1. Variation among ICUs in Unadjusted ABCDEF Bundle Performance Rates

adoption of elements B1, B2, and E (SATs, SBTs, and early mobility) proved far more challenging. For example, at the end of the Collaborative, an average $\leq 40\%$ of patients participated in early mobility and less than half of patients requiring MV received a daily SBT. Although overall performance was relatively poor, there were indeed some very good bundle performers.

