Setting and Sample. **Included** in the Collaborative were adults who were (1) initially admitted to a participating ICU and (2) designated as needing ICU level of care. Patients previously admitted to a non-participating ICU during their current hospitalization were not included. “ICU level of care” was defined as patients who (1) needed intensive medical and/or nursing care that not could not be delivered in a step-down and/or medical/surgical unit, (2) were managed by an ICU team, or (3) did not have transfer orders written or downgraded to a lower level of care. **Excluded** were patients who (1) died or were discharged within 24 hours of ICU admission or (2) were undergoing life support withdrawal and/or documented comfort care only within 24 hours of ICU admission.

Aim 1 data consist of **15,226** patients who spent 24 hours in a participating ICU (~**49,000 ICU patient-days**). Our sample includes patients on and off MV, ranging from 18-90+ years old, admitted with a variety of diagnoses. Of the 15,226 patients, 63% (n = 9619) were hospitalized in academic medical centers and admitted to mixed medical/surgical (56%), medical (18%), surgical/trauma (12%), neurologic (5%), or cardiac/surgical (10%) ICUs.

Procedures and Data Sources. The Vanderbilt University Medical Center Institutional Review Board (IRB) served as the Coordinating Center IRB and approved the SCCM ICU Liberation Collaborative QI project. All Collaborative participants acquired site-specific IRB evaluation and approval. No identifiable data were collected. All data were collected by standardized medical record review and anonymous staff surveys and were managed using a secure, web-based application designed for validated data entry, transmission, and storage (Research Electronic Data Capture [REDCap], Vanderbilt University, 2016 - grant support [(UL1 TR000445 from NCATS/NIH]).

[figure not shown]

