β_{1j} Month + β_{2j} Imp + β_{3j} Month * Imp + e_{ij} , where (1) Logit(Y_{ij}) denotes the logit (or log-odds) of receiving bundle performance for the i^{th} ICU-day of the j^{th} patient; (2) Month is the month indicator of the study period (a total of 20 months coded as -5 to 0 for pre-implementation period and 1 to 14 for implementation period); and (3) Imp denotes an indicator variable coded as 0 for pre-implementation period and 1 for the implementation period. Therefore, Logit(Y_{ij}) is modeled as a linear function of $\beta_{0j} + \beta_{1j}$ Month for the pre-implementation period and $(\beta_{0j} + \beta_{2j}) + (\beta_{1j} + \beta_{3j})$ Month for the implementation period. β_{2j} and β_{3j} are the estimates of level and slope changes due to the intervention implementation. A significant level change (β_{2j}) indicates an immediate change in the level of bundle performance at the initiation of intervention implementation. A significant slope change (β_{3j}) indicates different trends over time during the pre- vs. post-implementation periods. Under the multilevel modeling framework, level-2 models will fit β_{0j} , β_{1j} , β_{2j} , and β_{3j} each as a linear function of fixed-effects of patient characteristics and patient-specific random effects. The patient-specific random terms allow for adjustment of within-patient clustering of ICU-days. Take patient gender as an example. From the combined multilevel segmented logistic regression model, we will (1) estimate the overall trends during the pre- and implementation periods (solid black lines); (2) derive fixed-effect estimates by patient characteristics (Figure 4, long dashed line and short dashed line for each gender); (3) test the significance of hypothesized subgroup differences (e.g., older age, obese, and non-English speaking) in the these estimates; and (4) include patient-specific random terms to allow for variability by patients (patient-specific lines not shown in Figure 4). The model can be simplified if supported by the preliminary results. For example, if the initial analyses for an outcome (e.g., element E performance) suggest that (1) there are no significant level change and slope change for both male and female patients and (2) the overall increasing trend over time does not differ by patient gender, we can reduce the model to a parsimonious form using multilevel logistic regression to model the probability of having an outcome as a function of fixed effect of patient gender, fixed effect of time, and patient-specific random effects. We can also further extend the model to (1) include multiple patient characteristics simultaneously in the model to generate multivariable adjusted estimates, (2) perform curve fitting for linear or non-linear trend, and (3) adjust for additional clustering (e.g., within-organization clustering). The above desried multilevel segmented logistic regression approach will be applied to analyzing complete and element bundle performance measures. For proportional bundle performance, we will use multilevel segmented Poisson regression instead.

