
Power analysis. We used the simulated-based power calculation method by Zhang et al.¹³³ for interrupted time series analysis to conduct power analysis for Aim 1. With the expected ~49,000 ICU-days of ~15,000 patients in 68 ICUs, we generated 1,000 simulations with various patient subgroup distributions and proportion of ICU days with bundle performance during the pre-implementation and implementation periods. Our preliminary analyses of the pre-implementation period data suggest that the probability of bundle performance ranged from 0.05 (for complete bundle performance) to 0.60 (for performance of element A) at the end of the pre-implementation period and a monthly increase in the probability ranged from zero (for element E) to 0.05 (for element D). To be conservative in power calculation, we used a probability of 0.05 for the level and a 0.05 monthly increase in the probability for the slope in the pre-implementation period. Our power analysis suggested that our data will have 80% power to detect an odds ratio (OR) of 1.25 (corresponding to an increase of 0.02 in the probability of receiving bundle performance) and 80% power to detect a slope change, with an OR of 1.52 corresponding to pre- vs. post-difference of 0.03 in the monthly increase of the probability of receiving bundle care. Based on our preliminary data, we reasonably assumed an autocorrelation of 0.5 under the first order auto-regressive covariance structure, a within-patient correlation of 0.5, and a within-hospital correlation of 0.6 in our simulation-based power calculation. Under the same assumptions, we also conducted power analyses on the effects of patient characteristics on the level and slope changes. For patient characteristics with 20:80 distribution, our sample size will have 80% power to detect an OR of 1.73 for the effect of patient characteristics on level change and 80% power to detect an OR of 2.65 for the effect of patient characteristic on slope change. The above power calculation is the most conservative scenario. The study power will be greater than 80% for other cases (e.g., pre-probability of 0.5, patient characteristics with 50:50 distribution). Regardless of study power, we will report point estimates, 95% confidence intervals, and use clinical significance to guide results interpretation. All above calculations were based on multilevel segmented logistic regression with a 0.05 two-sided significance level and adjusted for data dependencies described above.

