Sample Size/Power Analysis. The reliability of ICU-specific performance rates depends on sample size in each hospital (ICU days after adjusting for within-patient clustering). Using the Spearman-Brown prophecy formula,^{138,139} a minimal sample size of 10 is needed to generate reliable ICU-specific estimates (reliability ≥ 0.8), assuming an intraclass correlation of 0.3 for between-ICU variation based on our preliminary analysis. Given the large number of observations in our data ($\sim 49,000$ ICU patient-days nested in $\sim 15,000$ patients in 68 ICUs), there will be sufficient sample size to generate an ICU-specific performance estimate with ≥ 0.8 reliability, even conservatively assuming a large within-patient correlation of 0.8. We conducted power analysis for the effects of organization-level characteristics using the same simulation-based approach described for Aim 1 power analysis. Under the most conservative scenario (see power analysis of Aim 1), our sample size will have sufficient power ($\geq 80\%$) to detect an OR of 1.80 for the effect of an implementation strategy (used vs. not used by the site) on level change and an OR of 2.96 for the effect of an implementation strategy in slope change, assuming 20:80 distribution of the implementation strategy (used vs. not used by the site).

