Missing data. All 68 ICUs before and 42 ICUs after the Collaborative completed the organizational survey. The advantages of the multilevel model for analyzing longitudinal data lie in its flexibility in handling missing data and more efficient use of available data. Multilevel modeling allows for varying numbers of waves of data per study unit; the same number of waves of data is not required for all hospitals. Thus, missing data will be more easily managed, and all available data will be used for model estimates. Nonetheless, we will carefully examine the extent and pattern of missing data and impute missing values when appropriate. If missing not at random exists, we will use pattern-mixture modeling. We will also conduct sensitivity analyses to examine the robustness of study findings with and without multiple imputation or using pattern-mixture modeling.

Aim 3: Determine which implementation strategies result in the greatest adoption of the ABCDEF bundle.

Design and Rationale. Identifying feasible and effective ABCDEF bundle implementation strategies that are contextually appropriate remains a challenge for ICU researchers and practicing clinicians. In Aim 3, we will extend data collection and use both quantitative and qualitative approaches (i.e., using an online survey, concept mapping exercise, and an expert panel) to gain a deeper understanding of which implementation strategies are most likely to overcome barriers to ABCDEF bundle adoption.

Setting and Sample. Healthcare providers from the 68 sites that participated in the ICU Liberation Collaborative will be included in the work outlined in Specific Aim 3. These healthcare providers will have experience working in one of the ICU Liberation Collaborative units and come from various professional groups (e.g., nursing, medicine, pharmacy, physical/occupational/respiratory therapy). We will also include a subgroup of 10-12 healthcare providers who currently serve of the SCCM's ICU Liberation and/or Quality and Safety committee and two members of the SCCM's Council who are responsible for overseeing the society's quality & safety initiatives in an expert panel.

Procedures and Data Sources.

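### The Aim 1 power scenario is not the most conservative one, and the promise of more than 80% power in other cases is unsupported for rarer characteristics, flat low baselines and the 42-ICU post survey

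*Combined protocol and SAP*

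**What the plan says.** The Aim 1 power analysis is a simulation: "With the expected ~49,000 ICU-days of ~15,000 patients in 68 ICUs", two-sided alpha 0.05, within-patient correlation 0.5 and within-hospital correlation 0.6. It sets the pre-implementation level at 0.05 and the monthly rise at 0.05 and calls this choice conservative. For a patient characteristic split 20:80 it reports 80% power at OR 1.73 (level change) and OR 2.65 (slope change). It then concludes: "The above power calculation is the most conservative scenario. The study power will be greater than 80% for other cases". Its two examples of other cases, a pre-probability of 0.5 and a 50:50 split, are both easier.

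The Aim 2 power section reuses the scenario: "Under the most conservative scenario (see power analysis of Aim 1), our sample size will have sufficient power" for OR 1.80 (level) and 2.96 (slope), again at 20:80 and with 68 ICUs.

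Elsewhere the plan states:
- Aim 1 will "test the significance of hypothesized subgroup differences (e.g., older age, obese, and non-English speaking"). No shares are given for these groups.
- Observed monthly rises ran from zero (element E) to 0.05 (element D). Preliminary Data puts baseline complete-bundle performance below 4% with a relatively flat trend.
- "All 68 ICUs before and 42 ICUs after the Collaborative completed the organizational survey". Aim 2 uses the post survey to model level change and slope change.

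**The concern.** The claim is general: no planned analysis is harder than the one simulated, and all others have more than 80% power. One harder planned case is enough to defeat it. A characteristic rarer than 20% carries less information. A flat baseline near 0.04 carries less than one climbing by 0.05 per month. An organizational predictor known for 42 ICUs carries less than one known for 68.

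What is at stake is the reading of null results. A non-significant finding for a small patient group, for an organizational feature taken from the post survey, or for the complete bundle itself would be set against a printed assurance of 80% power or more that the plan has not shown.

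**Working it through.** **1. Reproducing the plan's figures.** The simulation is not described fully enough to rebuild: how the correlations enter and what happens after implementation are not given. Two partial checks are possible.

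Internal consistency. Implied SE = ln(OR)/(1.960 + 0.842). A 20:80 modifier should multiply the overall SE by 1/√(0.2 × 0.8) = 2.5.
- Level: ln 1.25 = 0.223; × 2.5 = 0.558; OR 1.75 against 1.73 stated. Power at 1.73 is 78.6%, so the figures agree.
- Slope: ln 1.52 = 0.419; × 2.5 = 1.047; OR 2.85 against 2.65 stated. Power at 2.65 is 74%, so they do not agree. No slope figures are scaled below.

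A rebuild from the information matrix is in step 4.

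**2. Rarer characteristics (Aim 1, level change).** Accept 80% at OR 1.73 and 20:80. For share p, the SE grows by k = √(0.16/[p(1−p)]). Power at OR 1.73 = Φ(2.802/k − 1.960); detectable OR = 1.73^k.

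| Share (assumed) | k | Power at OR 1.73 | OR at 80% power |
|---|---|---|---|
| 5% | 1.835 | 33% | 2.73 |
| 10% | 1.333 | 56% | 2.08 |
| 20% (plan) | 1.000 | 80% | 1.73 |
| 30% | 0.873 | 89% | 1.61 |
| 50% | 0.800 | 94% | 1.55 |

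**3. Forty-two ICUs (Aim 2, level change).** Taking ICUs as equally informative, k = √(68/42) = 1.272. Power at OR 1.80 = Φ(2.802/1.272 − 1.960) = Φ(0.242) = 60%. Detectable OR = 1.80^1.272 = 2.11.

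**4. Baseline level and trend.** The Aim 1 text describes 0.05 as a level at the end of the pre-period. Read literally, a rise of 0.05 per month up to that point gives −0.20, −0.15, −0.10, −0.05 and 0.00 in months −5 to −1, which is impossible. Starting at 0.05 in month −5 gives 0.30 by month 0. Information per ICU-day is proportional to P(1−P), which is 0.21 at P = 0.30 but 0.0475 at P = 0.05. The assumed rise therefore adds power.

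To size this, take the information matrix of the plan's segmented logistic model (intercept, month, implementation, month × implementation) over months −5 to 14, with:
- patients per ICU per month in the ratio 5 (baseline) to 15 (implementation), at 3.3 days each;
- design effect 1 + (3.3 − 1) × 0.5 = 2.15 for within-patient correlation;
- no separate ICU term, and probabilities capped at 0.95;
- the 20:80 modifier multiplying the level-change SE by 2.5.

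Two totals bracket the sample: 15,226 × 3.3 = 50,246 days, and nominal accrual of 68 × (6 × 5 + 14 × 15) = 16,320 patients × 3.3 = 53,856 days. Power = Φ(ln 1.73/SE − 1.960), with ln 1.73 = 0.548.

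| Baseline | SE, 20:80 (50,246 days) | Power | Power (53,856 days) |
|---|---|---|---|
| 0.05 at month −5, +0.05/month | 0.211 | 74% | 77% |
| Flat 0.05 | 0.413 | 26% | 28% |
| Flat 0.04 | 0.459 | 22% | 23% |

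With 50,246 days, the first row gives detectable ORs of 1.27 overall and 1.81 at 20:80, near the plan's 1.25 and 1.73. It is the closest reading found, though not an exact match.

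**5. Ventilated-only elements.** Preliminary Data reports SBT among patients requiring ventilation, while the sample includes patients on and off it. With ventilated share s and baseline rate b, relative information is f = s × b(1−b)/0.0475, and power = Φ(2.802√f − 1.960). At an assumed s = 50%:
- b = 0.05: f = 0.50, power 51%
- b = 0.10: f = 0.95, power 78%
- b = 0.20: f = 1.68, power 95%

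The documents give neither s nor b, so the direction is open.

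**The case against.** The wording may mean only the hardest of the cases simulated, since various subgroup distributions were tried. The Aim 2 section states its 20:80 assumption openly and does not repeat the promise about other cases. The Aim 1 and 2 data already exist, so no sample-size decision depends on the claim. The plan also undertakes to report estimates and 95% confidence intervals whatever the power. These points limit the consequence. They do not make the claim true: the simulated grid is not listed, the promise about other cases is unrestricted, and a zero monthly rise lies within the plan's own observed range.

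Several stronger readings are tempting but not supported:
- *The named subgroups have 33% to 56% power.* No shares are given. Older and obese patients may well exceed 20%, and shares between 20% and 80% keep at least 80% power on this scaling.
- *The ICU types supply the missing shares.* The sample description lists "surgical/trauma (12%), neurologic (5%), or cardiac/surgical (10%) ICUs", but these are shares of patients. ICU type comes from the Organizational Survey and is not among the Aim 1 patient variables, so they give neither a patient-characteristic split nor a split of ICUs.
- *SAT and SBT are underpowered.* That holds only if the baseline rate stays near 0.05 or few days are ventilated. A ventilated denominator is stated for SBT and is only probable for SAT.
- *Aim 3 has 42 sites.* That count belongs to the Aim 2 post organizational survey. Response to the Aim 3 strategy survey is unknown.
- *Aim 2 as a whole has 60% power.* The pre survey covers all 68 ICUs and also models level and slope change, and imputation is allowed where appropriate.

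**Conclusion.** The claim that this is the hardest case, with more than 80% power everywhere else, is wrong as written. The fault is over-claimed wording. The stated 80% has not been shown to be miscalculated: it was taken as true for the scaling and could not be rebuilt exactly.

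All else equal, characteristics rarer than 20% fall below 80% power at OR 1.73, to about 56% at an assumed 10% and 33% at an assumed 5%. Characteristics from the post organizational survey have about 60% power at OR 1.80, with a detectable OR of about 2.11, if the analysis is confined to the 42 responding ICUs. The baseline trend may matter most because it affects the complete-bundle outcome directly: about 74-77% under the assumed rise against 22-28% with a flat 0.04-0.05 baseline. Those last figures are approximate and rest on the simplifications listed in the working. For ventilated-only elements, no conclusion can be drawn until the ventilated days and baseline rates are reported.

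**What to change.** In the Aim 1 power analysis, remove both the description of the scenario as the most conservative and the promise of more than 80% power in other cases. Remove the matching description in the Aim 2 power section. Rerun the simulation and report detectable ORs for:
- characteristic shares of 5%, 10% and 20%;
- a flat baseline of 0.04-0.05 beside the rising one, stating the month to which the 0.05 level refers;
- the actual number of ventilated ICU-days, with their observed SAT and SBT baseline rates;
- 42 and 68 ICUs, plus the number of sites that respond to the Aim 3 survey once known.

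Label every assumed share as an assumption; where the database holds the real share, use it. The cost is a modest rerun, one small table and less favourable stated figures. No new patients and no design change are needed.

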Local staff who attended a training webinar and as-needed support from SCCM managers entered de-identified data into the collaborative database at their individual hospitals. Data were collected retrospectively during a 6-month baseline period (January 2015-June 2015) and prospectively during a 14-month implementation period (January 2016-March 2017). During the baseline (pre-Collaborative) period, staff from each site entered data on the first 5 consecutively admitted ICU patients each month (30 baseline patients per site). Throughout the implementation period, site staff collected data on the first 15 consecutively admitted patients per month. For each patient, daily data were collected for a maximum of seven ICU days (average of 3.3 ICU-days per patient) or until patients transferred out of the ICU, were designated non-ICU status, or died.

Measures. Patient-level variables include: age, sex, race, ethnicity, language, body mass index (BMI), admitting diagnosis, severity of illness, and preadmission residence and mobility status. The severity of illness scores collected in the Collaborative included the Acute Physiology and Chronic Health Evaluation (APACHE) II,¹³⁰ APACHE III,¹³¹ and APACHE IV¹³² referent to the patient's status at the time of ICU admission.

Data analysis. We will conduct similar analyses for each of the performance measures (performed vs. not performed), including complete, proportional, and each element performance. We will first use descriptive statistics to examine data distribution, check for outliers, and summarize patient characteristics. Bivariate tests (e.g., *t* test or Chi-square statistics) will be used to compare patient characteristics in the pre-Collaborative and Collaborative periods.

Using multilevel segmented logistic regression modeling for interrupted time series data, we can model the likelihood of bundle performance change over time, both before and during the periods of Collaborative implementation. **Figure 2** shows a hypothetical example. The basic form of the level-1 model (Figure x, solid black line) can be written as $\text{Logit}(Y_{ij}) = \beta_{0j} +$

Figure 2. Segmented logistic regression for ITS data-A hypothetical example

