Data Analysis. The overall analytic strategy for Aim 2 will be the same as described for Aim 1. That is, using multilevel segmented logistic regression modeling for complete and element bundle performance and multilevel segmented Poisson regression for proportional performance. First, we will examine the variation across ICUs in bundle performance by adding ICU-specific random effects to the model. All significant patient-level characteristics from Aim 1 will remain in the model as covariates so that ICU-level estimates are risk-adjusted for patient case mix. From the model, we can (1) quantify the degree of ICU variation using the intra-class correlation (ICC); (2) derive the ICU-specific adjusted rates of bundle performance at the last month of implementation and examine their distribution (mean, variance, median, interquartile range, and range); and (3) rank the ICU-specific adjusted rates from low to high and identify the top 5 and bottom 5 ICUs with best and worst adjusted performance rates. Next, we will estimate the effects of organizational characteristic on bundle adoption by adding them as fixed effects to the model. Organizational survey at the post-implementation period will be estimated as fixed effects to model the level change (β_{2j}) and slope change (β_{3j}). While data from the pre-implementation period will be estimated as fixed effects to model pre-implementation level (β_{0j}), pre-implementation slope (β_{1j}), post-implementation level change (β_{2j}), and slope change (β_{3j}) (see **Data Analysis section for Aim 1**). Again, multilevel clustering (within-patient clustering of ICU days and within-ICU clustering of patients) will be adjusted in the model using random effects terms. As the provider-level data can be linked to specific ICUs, but not linkable to specific patient and patient ICU days, we will use multilevel modeling (level-1: time-point [pre- and post-survey], level-2: provider; level-3: ICU) to model the fixed effect of time, provider-level assessments (AITCS, HWEA,^{136,137} and ICU Care and Perceptions surveys), and their interactions on ICU-level adjusted performance rates. From the model, we can derive contrast estimates on the effect of change in

provider-level assessments on ICU-level bundle adoption. We will also extend the model to adjust for ICU-within-organization clustering.

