
Potential Problems and Alternative Approaches and Benchmarks for Success

Potential limitations of Aims 1 and 2 include the possibility of missing data and the large number of data elements to be analyzed. Our team has intimate knowledge of the database and the key measures we are using. We have collapsed the data into relatively broad categories based on the constructs/domains of the CFIR and will continue to refine these measures using the experience of the entire team. Should we find key elements missing, our continued relationship with the Collaborative sites will allow us to explore additional methods of addressing these limitations. While we have a rigorous plan to adjust for patient case mix in deriving ICU-level risk-adjusted bundle adoption rates, there will admittedly be unmeasured confounders (e.g., patient or caregiver preference) that may bias the ICU-level estimate. However, it is reasonable to expect that such unmeasured confounders will be distributed evenly across ICUs. Finally, there may be concern regarding our ability to recruit the necessary participants to complete the work proposed in Aims 3 and 4. As demonstrated in the sample **letters of support**, Collaborative members remain tremendously excited and committed to furthering the important work of bundle adoption.

Potential Pitfalls foreseen for Aim 4 are due to selection of high and low performing units for focus group participation will be based on data collected in 2015-2017, therefore unit characteristics may have changed and unit adherence may have improved or regressed since the data were collected. We also recognize that ICU environments and experiences in the care of mechanically ventilated patients are rapidly changing in response

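### Aim 2 picks its case-mix covariates by an undefined significance screen in Aim 1 instead of fixing them in advance, so some residual confounding of the ICU comparisons is possible

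*Combined protocol and SAP*

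**What the plan says.** Aim 2, Data Analysis, sets the adjustment in one sentence: "All significant patient-level characteristics from Aim 1 will remain in the model as covariates". Its declared purpose is to correct the ICU results for differences in patient mix. From that model the investigators will estimate the ICC and then "rank the ICU-specific adjusted rates from low to high and identify the top 5 and bottom 5 ICUs". The same section adds organizational characteristics to the model and uses the adjusted ICU rates as the outcome of the provider-survey model. Aim 3, Data Analysis, analyses implementation strategies by the Aim 2 approach.

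The candidates are in Aim 1, Measures: "Patient-level variables include: age, sex, race, ethnicity, language, body mass index (BMI), admitting diagnosis, severity of illness, and preadmission residence and mobility status". That is ten characteristics.

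The plan leaves four things about the screen open:
- the threshold. A level appears only for the power calculation: "All above calculations were based on multilevel segmented logistic regression with a 0.05 two-sided significance level";
- which coefficient is tested (baseline level, baseline slope, level change or slope change);
- whether the test is univariable or multivariable, since Aim 1, Data analysis, offers the multivariable model only as a possible extension;
- whether one covariate set serves all performance measures or each measure has its own.

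No covariate is forced in, not even severity of illness, and no check of the ranks with the full set is planned. The section on potential problems says "we have a rigorous plan to adjust for patient case mix in deriving ICU-level risk-adjusted bundle adoption rates" and concedes only unmeasured confounders.

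**The concern.** A patient characteristic biases a comparison between ICUs to the extent that it affects bundle performance and is unevenly spread across ICUs. A significance test in Aim 1 measures neither. It mixes effect size with prevalence, outcome rate and sample size, and it says nothing about imbalance between ICUs. A characteristic with a real but modest effect can fail the test and still differ sharply between units.

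The adjusted rates carry much of the later inference: the ICC, the five best and five worst ICUs, the organizational effects, the provider-survey model and, through the shared approach, the Aim 3 strategy effects. The rule also sits oddly with the team's own practice. Under Preliminary Data, the earlier outcome analysis of the Collaborative data adjusted for at least 18 confounders chosen beforehand.

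**Working it through.** **1. The plan's nearest figure.** No figure is given for the covariate rule. The closest is the minimum of 10 observations per ICU for reliability of at least 0.8 at ICC 0.3 (Aim 2, Sample Size/Power Analysis). Spearman-Brown gives k = R(1 − ICC) / [ICC(1 − R)] = 0.8 × 0.7 / (0.3 × 0.2) = 9.33, rounded up to 10. It reproduces, and ICC 0.3 is used below.

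**2. Which main effects would the screen miss?** Inputs from the plan are 49,000 ICU-days, 3.3 days per patient, within-patient correlation 0.5, a 20:80 split and two-sided 0.05.

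- Effective sample size = 49,000 / [1 + (3.3 − 1) × 0.5] = 49,000 / 2.15 = 22,791.
- Odds ratio detectable with 80% power ≈ exp{2.802 / √[22,791 × 0.2 × 0.8 × p(1 − p)]}, where 2.802 = 1.960 + 0.842.
- At p = 0.50: exp(2.802 / √911.6) = exp(0.0928) = 1.10.
- At p = 0.05: exp(2.802 / √173.2) = exp(0.213) = 1.24. A two-proportion calculation gives 1.22.

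Less favourable cases, by the two-proportion calculation:
- a category held by 5% of patients, at a 5% rate: 1.42;
- an element assessed on only 30% to 50% of days (assumed), 20:80 split: 1.32 to 1.42 at a 5% rate and 1.14 to 1.18 at a 50% rate.

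These figures ignore clustering by ICU, so characteristics that vary mainly between ICUs would be harder to detect than shown.

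**3. How likely is some omission?** Suppose all ten characteristics had real effects, each detected with 95% power, independently (assumed). The chance of losing at least one is 1 − 0.95^10 = 0.40. At 80% power each it is 1 − 0.8^10 = 0.89. Losing something is plausible, so what matters is how much it moves the ranks.

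**4. How far do the ranks move?** Simulation of 68 ICUs without sampling error. The between-ICU SD on the logit scale is √[ICC/(1 − ICC) × π²/3], which is 1.19 at ICC 0.3 and 0.60 at an assumed ICC of 0.1. One binary covariate is dropped. Its prevalence across ICUs has mean 0.3 and SD 0.1 to 0.3 (assumed). The SD of the resulting shift relative to the between-ICU SD is ln(OR) × SD of prevalence / 1.19. That runs from ln(1.1) × 0.1 / 1.19 = 0.008 to ln(1.3) × 0.3 / 1.19 = 0.066.

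| ICC | OR of dropped covariate | SD of prevalence | ICUs unchanged, of 5 in each extreme group |
|---|---|---|---|
| 0.3 | 1.1 to 1.3 | 0.1 to 0.3 | 4.7 to 5.0 (rank correlation at least 0.996) |
| 0.3 | 1.73 to 2.0 | 0.1 to 0.3 | 4.3 to 4.8 |
| 0.1 (assumed) | 1.1 to 1.3 | 0.1 to 0.3 | 4.4 to 4.9 |
| 0.1 (assumed) | 1.73 to 2.0 | 0.3 | 3.8 to 4.1 |

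By step 2, covariates with odds ratios of 1.73 to 2.0 would rarely fail a main-effect screen over all ICU-days. The rows for 1.1 to 1.3 are the relevant ones for a single omission.

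**The case against.** The case against is substantial. The text says that significant characteristics stay; it does not say that the others go. With this many ICU-days, an important main effect will almost always pass, and what fails will hardly move the ranks. Forcing in every covariate is not free either: severity was recorded with three APACHE versions, admitting diagnosis has many categories, and the primary Aim 1 analysis uses complete cases.

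Most of this stands and limits the size of the point. It does not remove it. Significance is the only basis the plan gives for the adjustment, and a sentence about what will remain implies that something else will not.

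A reader might go further and take the plan's own power statement as proof that strong confounders will be missed: "our sample size will have 80% power to detect an OR of 1.73 for the effect of patient characteristics on level change". For slope change the corresponding odds ratio is 2.65. The documents do not support that reading. Those odds ratios concern how a characteristic modifies the level and slope changes, in what the plan calls its most conservative scenario. They do not describe main effects. The worked example in Aim 1, Data analysis, also drops the segmented terms when they are not significant and keeps the patient characteristic (gender) in the reduced model.

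**Conclusion.** The adjustment set is chosen by an undefined significance screen when it could be fixed in advance. Measured confounders can be left out, and residual case-mix confounding of the ICU results is possible beyond the unmeasured kind that the plan concedes.

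The likely size is modest. At ICC 0.3, one weak covariate dropped changes on average at most about 0.3 of the 5 ICUs in each extreme group (5 − 4.7). The effect is larger with several omissions, rare categories, low-rate or restricted-denominator elements, or an ICC below 0.3. The result rests on assumed spreads of case mix between ICUs, an assumed share of eligible days, no sampling error, and no allowance for ICU clustering in the detectable effects.

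A reader might infer that the rankings are under-adjusted as a matter of fact. The plan does not settle that. The basic Aim 1 model has patient random effects only, with clustering by organization as an optional extension. P values for characteristics that vary between ICUs may therefore be too small, and the screen may keep too many covariates. Nor do the documents show that specialised ICUs would be worst affected, that covariates will be selected separately for each measure, or that the SAT and SBT models use ventilated days only.

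**What to change.** Replace the sentence in Aim 2, Data Analysis, with: *Every patient characteristic listed in Aim 1, Measures, is kept as a covariate in all Aim 2 and Aim 3 models, whatever its P value in Aim 1.* State that severity enters as one harmonised term across the APACHE versions, and give the rule for harmonising it. Add mechanical-ventilation status only if it is in the dataset, because it is not among the listed measures.

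The cost is a few more parameters; with about 15,000 patients there is no sample-size reason to screen. Under complete-case analysis a few records may also be lost. The plan puts missingness in the Aim 1 data below 5%, and its multiple-imputation sensitivity analysis covers that loss. No new data are needed, and no power or sample-size figure changes.

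If the screen is kept, the minimum is to define it (threshold, coefficient, univariable or multivariable, one set or one per measure) and to report the ranks again with the full set.
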